5.4 Treatment Beyond Disease Progression

Accumulating evidence indicates a minority of participants treated with immunotherapy may derive clinical benefit despite initial evidence of PD.

Dosing of study treatment beyond ir-RECIST-defined disease progression is allowed for patients. Patients must meet all of the following criteria to be allowed to receive study treatment beyond disease progression:

- Evidence of clinical benefit (defined as the stabilization or improvement of disease-related symptoms) as assessed by the investigator
- Tolerance of study treatment
- Absence of symptoms and signs (including worsening of laboratory values; [e.g., new or worsening hypercalcemia]) indicating unequivocal progression of disease, despite a rising CEA level
- No decline in ECOG performance status that can be attributed to disease progression
- Absence of tumor progression at critical anatomical sites (e.g., leptomeningeal disease) that cannot be managed by protocol—allowed medical interventions
- Patients must provide written consent to acknowledge deferring other treatment options in favor of continuing study treatment at the time of ir-RECIST defined disease progression. All other

elements of the main consent including description of reasonably foreseeable risks or discomforts, or other alternative treatment options will still apply.

• Sponsor approval

Patients in whom radiographic disease progression is confirmed at a subsequent tumor assessment (within 6 weeks) may be considered for continued study treatment at the discretion of the investigator if they continue to meet the criteria above and have evidence of clinical benefit. The assessment of clinical benefit should be balanced by clinical judgment as to whether the participant is clinically deteriorating and unlikely to receive any benefit from continued treatment with study treatment.

5.5 Preparation/Handling/Storage/Accountability

The investigational products should be stored in a secure area according to local regulations. It is the responsibility of the investigator to ensure that investigational products are only dispensed to study Participants. The investigational products must be dispensed only from official study sites by authorized personnel according to local regulations. Vials of nivolumab injection must be stored at 2°C to 8°C (36°F to 46°F) and protected from light and freezing. The unopened vials can be stored at room temperature (up to 25°C, 77°F) and room light for up to 48 hours. The administration of nivolumab infusion must be completed within 24 hours of preparation. If not used immediately, the infusion solution may be stored under refrigeration conditions (2°C to 8°C, 36°F to 46°F) for up to 24 hours, and a maximum of 8 hours of the total24 hours can be at room temperature (up to 25°C, 77°F) and room light. The maximum of 8 hours under room temperature and room light conditions includes the product administration period.

Ipilimumab injection, 50 mg/10 mL (5 mg/mL) or 200 mg/40 mL (5 mg/mL), must be stored refrigerated (2°C to 8°C) and protected from light. Ipilimumab injection must not be frozen. Partially used vials or emptyvials of ipilimumab injection should be discarded at the site according to appropriate drug disposal procedures.

Ipilimumab injection may be stored undiluted (5 mg/mL) or following dilution in 0.9% Sodium Chloride Injection, USP or 5% Dextrose Injection, USP in PVC, non-PVC/non-DEHP, or glass containers for up to 24 hours at 2°C to 8°C or room temperature/room light.

Recommended safety measures for preparation and handling include protective clothing, gloves, and safety cabinets.

If concerns regarding the quality or appearance of the study treatment arise, the study treatment should notbe dispensed and contact the Sponsor immediately. Study treatment not supplied by the Sponsor will be stored in accordance with the package insert and IB: Temozolomide will be stored at room temperature (upto 25°C, 77°F). Investigational product documentation (whether supplied by the Sponsor or not) must be maintained that includes all processes required to ensure drug is accurately administered. This includes documentation of drug storage, administration and, as applicable, storage temperatures, reconstitution, and use of required processes (e.g., required diluents, administration sets).

5.6 Concomitant Treatments

5.6.1 Permitted Treatments

Concomitant therapy includes any prescription medications or over-the-counter preparations used by apatient between the 7 days preceding the screening evaluation and the treatment discontinuation visit. Any concomitant therapy administered during this period should be recorded on the appropriate eCRF.

Patients who experience infusion-associated symptoms may be treated symptomatically with acetaminophen, ibuprofen, diphenhydramine, and/or famotidine or another H2 receptor antagonist, as per standard practice. Serious infusion-associated events manifested by dyspnea, hypotension, wheezing, bronchospasm,

tachycardia, reduced oxygen saturation, or respiratory distress should be managed with supportive therapies as clinically indicated (e.g., supplemental oxygen and β 2-adrenergic agonists).

Participants are permitted the use of topical, ocular, intra-articular, intranasal and inhalation corticosteroids (with minimal system absorption).

Adrenal replacement steroid doses > 10 mg daily prednisone are permitted. A brief (less than 3 weeks) course of corticosteroids for prophylaxis (e.g., for contrast dye allergy) or for treatment of non-autoimmune conditions (e.g., delayed-type hypersensitivity reaction caused by a contact allergen) is permitted.

Premedication for NIVO and IPI may be administered for Cycles ≥ 2 at the discretion of the treating physician after consultation with the Sponsor.

The use of inhaled corticosteroids and mineralocorticoids (e.g., fludrocortisone) for patients with orthostatic hypotension or adrenocortical insufficiency is allowed. Megestrol administered as an appetite stimulant is acceptable while the patient is enrolled in the study.

Influenza vaccination should be given during influenza season only (approximately October to March). Patients must not receive live, attenuated influenza vaccine within 4 weeks prior to Cycle 1, Day 1 or at any time during the study but may receive inactivated vaccines.

Patients who use hormonal therapy with oral contraceptives, hormone-replacement therapy, prophylactic or therapeutic anticoagulation therapy (such as low-molecular weight heparin or warfarin at a stable dose level), or other allowed therapy should continue their use.

Males and females of reproductive potential should use highly effective means of contraception.

Prior palliative radiotherapy must have been completed at least 2 weeks prior to first dose.

5.6.2 Prohibited and/or Restricted Treatments

The following medications are prohibited during the study (unless utilized to treat a drug-related adverse event). Medications taken within 2 weeks prior to initial study drug administration and medications taken during study must be recorded on the CRF.

- Immunosuppressive agents, including but not limited to cyclophosphamide, azathioprine, methotrexate, and thalidomide.
- Immunosuppressive doses of systemic corticosteroids (except as stated in Section 5.6.1)
- Any concurrent antineoplastic therapy (i.e., chemotherapy, hormonal therapy, immunotherapy, extensive, non-palliative radiation therapy, or standard or investigational agents for treatment of cancer)
- Any botanical preparation (e.g. herbal supplements or traditional Chinese medicines) intended totreat the disease under study or provide supportive care. Use of marijuana and its derivatives for treatment of symptoms related to cancer or cancer treatment are permitted if obtained by medical prescription or if its use (even without a medical prescription) has been legalized locally.
- Any live / attenuated vaccine (e.g. varicella, zoster, yellow fever, rotavirus, oral polio and measles, mumps, rubella (MMR)) during treatment and until 100 days post last dose.
- Initiation or increased dose of granulocyte colony-stimulating factors (e.g., granulocyte colony-stimulating factor, granulocyte/macrophage colony-stimulating factor, and/or pegfilgrastim) is strongly discouraged.
- Patients are not allowed to receive immunostimulatory agents, including but not limited to IFN- α , IFN- γ , or IL-2, during the entire study.
- All patients (including those who discontinue the study early) should not receive other immunostimulatory agents for 10 weeks after the last dose of NIVO and IPI.

Participants with a condition requiring systemic treatment with either corticosteroids (> 10 mg daily prednisone equivalent) or other immunosuppressive medications within 14 days of treatment assignment are excluded. Inhaled or topical steroids, and adrenal replacement steroid doses > 10 mg daily prednisone equivalent, are permitted in the absence of active autoimmune disease.

Any concomitant therapy intended for the treatment of cancer, whether health authority approved or experimental, is prohibited during the study period. This includes but is not limited to the following:

• Chemotherapy, hormonal therapy, immunotherapy, radiotherapy, investigational agents, or herbal therapy

After the completion of Cycle 1, palliative radiotherapy may be considered if patients are deriving benefit (e.g., treatment of known bone metastases).

Patients experiencing a mixed response requiring local therapy (e.g., surgery, stereotactic radiosurgery, radiotherapy, radiofrequency ablation) for control of three or fewer lesions may still be eligible to continue study treatment, after the approval of the Sponsor. Patients who receive local therapy directed at a target lesion will no longer be evaluable for radiographic response but will remain evaluable for progression.

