10 STATISTICAL CONSIDERATIONS

10.1 Sample size determination

This is an open-label, multicenter, single-arm Phase II trial designed to estimate the activity of TMZ in association with NIVO and IPI in MGMT silenced, MSS, advanced CRC patients who have progressed after irinotecan, oxaliplatin, fluoropyrimidines and anti-EGFR mAbs (in *RAS/BRAF* wild type tumors).

According to our previously published results, in MGMT methylated mCRC with initial clinical benefit from TMZ (CR+PR+SD at 8 weeks) the individual PFS is almost always shorter than 6 months, and therefore the median PFS falls between 16- and 24-week reassessments. Therefore, after the first 8-week CT scan reassessment, by adding NIVO and IPI to TMZ, we plan to increase the 8-month PFS rate estimated by the Kaplan-Meier Method from 5% to 20%, with an alfa-error of 0.05 and a beta-error of 0.20.

According to the Fleming single-stage design and selecting the design parameters p0 (8-months PFS rate in the null hypothesis) = 0.05*, and p1 (8-months PFS rate in the alternative hypothesis) = 0.20, respectively, a total of 27 patients will be required. Null hypothesis will be rejected if at least 4 patients will be progression-free at the 8-months reassessment.

- *A null hypothesis of 0.05 is based on the consideration that single agent TMZ does not lead to individual PFS times beyond 6 months in the refractory setting.
- **The alternative hypothesis of 0.20 is considered as a potential target of interest for further studies in this setting with the experimental treatment.

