10.4 Progression Free Survival as determined by Investigator per RECIST v1.1 and Ir-RECIST

PFS is defined as the time from the first dose of TMZ to time of disease progression per RECIST v1.1 and Ir-RECIST as determined by the investigator or death due to any cause on study, whichever occurs first. Patients who have not experienced disease progression and are alive at the time of analysis will be censored at the time of the last tumor assessment.

The Kaplan-Meier method will be used to estimate PFS. The 95% CIs for median PFS were computed using the Brookmeyer and Crowley method. *Patients with no post-baseline tumor assessment will be censored at the time of first dose plus 1 day.*

A patient is considered to have disease progression by ir-RECIST if either of the following conditions is met:

- a) Ir-RECIST criteria for progression were met at a tumor assessment and no subsequent tumor assessment was performed
- b) Ir-RECIST criteria for progression were met at a tumor assessment and at the subsequenttumor assessment the criteria for confirmed progression by ir-RECIST were also met

For patients who meet criterion a), the date of progression is the date of the tumor assessment that met the criteria for ir-RECIST. For patients who meet criterion b), the date of progression is the date of the tumor assessment at which the ir-RECIST criteria for progression were first met. Patients who do not meet either of the above criteria are not considered to have had disease progression by ir-RECIST.

Patients who have not experienced disease progression and are alive at the time of analysis will be censored at the time of the last tumor assessment. The Kaplan-Meier method will be used to estimate PFS. The 95% CIs for median PFS will be computed using the Brookmeyer and Crowley method. Patients with no post-baseline tumor assessment will be censored at the time of first dose plus 1 day.

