Sum of the Diameters at Tumor Assessment: For every on-study tumor assessment collected per protocol or as clinically indicated, the sum of the diameters at tumor assessment will be calculated using tumor imaging scans. All target lesions and all new measurable lesions that have emerged after baseline will contribute to the sum of the diameters at tumor assessment. Hence, each net percentage change in tumor

burden per assessment with use of ir-RECIST accounts for the size and growth kinetics of both old and new lesions as they appear.

Note: In the case of new lymph nodes, RECIST v1.1 criteria for measurability (equivalent to baseline target lesion selection) will be followed. That is, if at first appearance the short axis of a new lymph node lesion ≥ 15 mm, it will be considered a measurable new lesion and will be tracked and included in the SLD. Thereafter, the lymph node lesion will be measured at subsequent timepoints and measurements will be included in the SLD, even if the short axis diameter decreases to < 15 mm (or even < 10 mm). However, if it subsequently decreases to < 10 mm, and all other lesions are no longer detectable (or have also decreased toa short axis diameter of < 10 mm if lymph nodes), then a response assessment of CR may be assigned.

If at first appearance the short axis of a new lymph node is ≥ 10 mm and < 15 mm, the lymph node will not be considered measurable but will still be considered a new lesion. It will not be included in the SLD unless it subsequently becomes measurable (short axis diameter ≥ 15 mm).

The appearance of new lymph nodes with diameter < 10 mm should not be considered pathological and not considered a new lesion.

RESPONSE CRITERIA

Evaluation of Target Lesions

Complete Response (CR): Disappearance of all target lesions. Lymph nodes that shrink to < 10 mm short axis are considered normal.

Partial Response (PR): At least a 30% decrease in the sum of the diameters of all target and all new measurable lesions, taking as reference the baseline sum of diameters, in the absence of CR.

Note: the appearance of new measurable lesions is factored into the overall tumor burden, but *does not* automatically qualify as progressive disease until the sum of the diameters increases by $\geq 20\%$ when compared with the sum of the diameters at nadir.

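### Local treatment of a growing lesion is allowed and the patient stays in the progression analysis, but no rule says how this counts in the 4-of-27 decision

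*Protocol*

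**What the plan says.** Section 5.6.2 opens its second list with a general ban: "Any concomitant therapy intended for the treatment of cancer, whether health authority approved or experimental, is prohibited during the study period". Exceptions follow directly. One of them allows local therapy, such as surgery, radiosurgery, radiotherapy or ablation, for control of at most three lesions in a patient with a mixed response. Sponsor approval is required and study treatment may go on. The term mixed response is not defined. On the endpoints the section says: "Patients who receive local therapy directed at a target lesion will no longer be evaluable for radiographic response but will remain evaluable for progression".

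The primary endpoint in 10.2.1 is PFS at 8 months, assessed by the investigators, with progression or death as the only events. The censoring rules in 10.4 and 10.9 do not mention local therapy. For ir-RECIST, 10.4 accepts a progression only if no later scan was done (a) or if the next scan meets the criteria again (b), and adds: "Patients who do not meet either of the above criteria are not considered to have had disease progression by ir-RECIST". Appendix II builds the ir-RECIST tumour burden as follows: "All target lesions and all new measurable lesions that have emerged after baseline will contribute to the sum of the diameters at tumor assessment".

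The decision rule in 10.1 is: "Null hypothesis will be rejected if at least 4 patients will be progression-free at the 8-months reassessment".

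**The concern.** A lesion picked for local control in a mixed response is likely to be one that is growing. Treating it removes tissue that might have produced the progression event. The protocol recognises that local therapy spoils lesion measurement, because it withdraws the patient from the response analysis. It gives no matching protection to PFS, which carries the primary decision.

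The trial is open-label and single-arm, with local reading of the primary endpoint. Without a control arm, nothing offsets a success that is owed to surgery or ablation rather than to the drug combination. With a threshold of 4 patients, one such case can decide the trial.

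**Working it through.** **1. The plan's own figure.** Inputs from 10.1: "p0 (8-months PFS rate in the null hypothesis) = 0.05", "p1 (8-months PFS rate in the alternative hypothesis) = 0.20", "with an alfa-error of 0.05 and a beta-error of 0.20", 27 patients, at least 4 successes. Let X be binomial.

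- P(X ≥ 4 | n = 27, p = 0.05) = 0.0437
- P(X ≥ 4 | n = 27, p = 0.20) = 0.818

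A search for the smallest n with exact one-sided alpha at most 0.05 and power at least 0.80 returns n = 27 with threshold 4. The stated design is reproduced.

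**2. One true failure counted as a success.** There are two ways to compute this, both at p = 0.05 and both conditional on the conversion happening:

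- Fix one patient as a success, so that 3 of the other 26 suffice: P(X ≥ 3 | 26) = 0.139.
- Let any failure among the 27 be turned, so that 3 true successes suffice: P(X ≥ 3 | 27) = 0.0437 + P(X = 3) = 0.0437 + 0.1068 = 0.150.

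With two patients fixed as successes, P(X ≥ 2 | 25) = 0.358.

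**3. A share q of true failures converted (q is assumed).** The success probability becomes 0.05 + 0.95q.

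| q | success probability | P(X ≥ 4 of 27) |
|---|---|---|
| 1% | 0.0595 | 0.074 |
| 2% | 0.069 | 0.112 |
| 3% | 0.0785 | 0.158 |
| 5% | 0.0975 | 0.267 |
| 10% | 0.145 | 0.564 |

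**4. Route under RECIST 1.1.** Appendix III requires a rise of at least 20% and 5 mm over the smallest sum, a new lesion, or unequivocal non-target progression. If any of these is documented before the procedure, the PFS event is fixed. Growth short of the threshold is not an event, and a lesion that has been removed cannot reach the threshold later.

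**5. Route under ir-RECIST (lesion sizes assumed).** Baseline and smallest sum are 100 mm. Targets shrink to 85 mm and two new measurable lesions total 36 mm. The sum is 85 + 36 = 121 mm, or +21%, a first ir-RECIST progression. Both new lesions are ablated and scored 0 mm. The next sum is 85 mm, or −15%, so neither (a) nor (b) of 10.4 is met and no progression is recorded. Under RECIST 1.1 the same patient progressed when the new lesions appeared (Appendix III, Table 12).

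**6. Which criterion defines the primary endpoint.** Section 10.2.1 names none. Section 3.5.1 lists PFS by RECIST 1.1 and by ir-RECIST ahead of the secondary measures. Section 10.2.2 lists both as secondary. Step 5 therefore touches the primary decision on one reading only.

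**7. Response.** The restriction covers target lesions only. Under ir-RECIST, suppose targets shrink by 30%, to 70 mm, beside 36 mm of new lesions. The sum is 106 mm, which is not a partial response. Once the new lesions are treated and scored 0 mm it is 70 mm, or −30%, which is one. Clearing the last non-target lesion does not change ORR: with targets in complete response the patient is already a partial responder (Tables 11 and 12).

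**8. Cost of counting these patients as failures.** With one or two patients forced to failure, power at p = 0.20 is P(X ≥ 4 | 26) = 0.793 or P(X ≥ 4 | 25) = 0.766, against 0.818. The type I error stays at or below 0.0437.

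**The case against.** Several stronger readings are tempting, and the document does not support them.

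- *That locally treated patients count as progression-free.* The text says they stay evaluable for progression, so they can still fail. The ir-RECIST example in the working is a failure under RECIST 1.1 from the first new lesion.
- *That the bias can only favour success.* If a removed target lesion is scored 0 mm, the smallest sum falls and growth elsewhere reaches +20% sooner. Neither appendix says how to score a lesion removed or ablated on study.
- *That 5.6.2 flatly contradicts itself.* It is mostly a ban followed by stated exceptions. Section 6.1 stops treatment for non-protocol anti-cancer therapy, and therapy permitted in 5.6.2 can be read as within protocol.
- *That local therapy must be a PFS event in the primary analysis.* Sections 3.1.1, 3.1.3 and 7.6.2 keep following patients who start new cancer therapy without progression. The clause in 5.6.2 fits that treatment-policy approach. Making local therapy an event is a different estimand, and it costs power.

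It is also fair that a converted patient must stay progression-free to month 8 with every untreated lesion holding, that Sponsor approval limits access, that centrally assessed PFS gives a partial check, and that a statistical analysis plan could add a rule.

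These points narrow the concern without removing it. Sponsor approval governs who gets the procedure and not how the outcome is scored. Central readers applying the same criteria would see the same altered lesions. The protocol itself, not a later plan, fixes that these patients remain in the progression analysis.

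**Conclusion.** The concern holds in a limited form. There is a route under RECIST 1.1 (treatment while growth is below the threshold) and a more direct one under ir-RECIST (treatment between first progression and the confirming scan). By either, local therapy can leave a patient progression-free at 8 months who would otherwise have failed. The second reaches the primary decision only if ir-RECIST defines it, which 10.2.1 leaves open.

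One such patient raises the exact false-positive rate from 0.044 to 0.139 or 0.150, depending on how the conversion is modelled. The number of patients who would receive local therapy, and the share who would then stay progression-free to month 8, are not given. One patient, two patients, and the 1% to 10% range are assumptions. The figures show how sensitive a threshold of 4 is. They do not predict what will happen.

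**What to change.** Leave the clinical permission as the sponsor wants it and change the following.

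1. In 10.4, state that a first ir-RECIST progression stands if local therapy to any lesion is given before the next scan.
2. In 5.6.2, extend the loss of response evaluability to new lesions that enter the ir-RECIST sum, for scans after the procedure, and keep these patients in the ORR denominator.
3. Pre-specify an analysis of the 4-of-27 decision in which patients given local therapy for disease control before 8 months count as not progression-free, and report it beside the primary result. Record the date and site of local therapy on the eCRF.
4. Clarify how the ban in 5.6.2, its exceptions and the stop for non-protocol therapy in 6.1 fit together.

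The cost is a few sentences and perhaps one data field, since 5.6.1 defines concomitant therapy as medications and may not capture surgery or ablation. The sensitivity result will be somewhat less favourable: power 0.793 or 0.766 if one or two patients are forced to failure. The sample size and the threshold need not change.
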